3.4 Statistical Methods

Sample Size Determination:

The study has been designed to detect superiority of the test product (Octanediol 1% Solution) over placebo in clinical use. It is known that octanediol 5% is effective to eliminate an established head louse infestation. However, it was also observed during the original in vitro studies of 1,2-octanediol that solutions containing 1% active material were able to kill lice, albeit more slowly, and inhibit them from laying eggs.

This suggests that regular use may prevent an infestation from developing in about 60%-70% of users over a period of a school term, whereas people at similarly high risk of infestation who take no action, or as in this study use placebo, might be expected to go through a school term without infestation in about 25%-35% of cases.

The structure and size of this study are based on parameters that are not normally considered in clinical investigations. Unlike most clinical investigations, the participants in this study do not already have a treatable condition. The aim is to prevent a treatable condition but is unlike other “preventive” studies, e.g. vaccine trials, in that those are normally long-term population studies engaging large numbers of participants with a quite small potential for detectable failure overall.

In order to address a number of unknown factors related to the risk of infestation, estimations for this risk have been made based on a calculated overall risk for the population as a whole. For this a number of estimations were based on public domain information and experience obtained in earlier clinical studies (there are no published independent data of incidence or prevalence for this infestation available). The estimation for incidence of risk of infestation is as follows:

The number of units of head louse treatments sold annually in the UK is approximately 2.5 million. Therefore, the number of units of head louse treatments sold weekly is approximately 49,145

It was estimated that approximately 50% of these are for new infestations in children, i.e. the remaining 50% of units are for adults or infants or either for retreatment after failure to cure or are additional purchases as part of a 2x application treatment regimen. Therefore, the number of new cases of head louse infestation is actually approximately 24,572 per week. And as there are approximately 5.4 million children in the highest “at risk” age group in the UK (4-13 years) this means that approximately 0.455% of children become infested each week.

In order to relate these data to this study it is known that the child population of Cambridgeshire in the “at risk” age group is about 51,000, which means that approximately 232 cases of head louse infestation occur in the whole of Cambridgeshire each week.

Two approaches to the study size estimation were considered, a straightforward

comparative study of two groups or a cross-over study using a survival analysis consideration, with each participant acting as his or her control. The arguments in favour of the cross-over model appear stronger in that smaller numbers of participants can be engaged, to minimise exposure to the new preparation, and it also offers internal controlling, with each participant acting as his or her control (with the assumption that the individual's risk remains more or less constant over the relatively short time of the study). The risk factors for each individual are sufficiently unknown that randomisation alone may not wholly address any disparity in infestation risk due to social and family circumstances, especially in a relatively small study cohort. Therefore, self-controlling for each individual is an attractive option to avoid any skew resulting from these unknown factors. By using a cross over study it would be possible to use a survival analysis approach in relation to time to first infestation (see **Analytical Methods**, below).

Calculations were made to investigate the possibility of using the cross-over estimations to limit participant numbers, for example to say 15 per group. However, when the "incidence" figures above were applied, it was found that it would be likely it would be impossible to make a reliable comparison between the product and placebo because of the possible low rate of infestation in the population as a whole.

In order to partially address the problems outlined above it is planned to mostly recruit from contacts, obtained from previous clinical studies, who have expressed an interest to take part in a study of this type. This group is known to be more at risk. Therefore, based on past study data relating to when people have contracted lice after study treatments, there is a reasonable expectation of an infestation rate of between 3 and 5 instances of reinfestation per year for each person in that group, i.e. a risk of about 3.6-4 possible reinfestation events per week for the whole study population. This doesn't mean that they will get lice but rather that they could come into contact with someone who does have them and lice could therefore be passed to them.

An estimation of sample size was made using conventional "survival analysis" calculations and the table below is taken from http://www.stattools.net/SSizSurvival_Pgm.php.

The table of sample size for 2 survival ratios is applicable to the common situation where the probability of Type I error $\alpha = 0.05$ (95% confidence) and power = 0.8 (80% power). In conventional survival analysis terms it assumes that the sample size in each of the two arms is the same, which in this case is certainly correct because each individual participates in both treatment arms sequentially.

The rows and columns represent the anticipated proportions of participants remaining louse free in each of the two treatment arms, and each cell is the total sample size (both treatment arms together) for that row/column combination. The shading covers the anticipated range of outcomes. These estimations of size that are proposed for this study appear to be at around the lower bound of population size required for the 30-35% difference in outcome between treatments necessary to detect superiority (range 62-90 participants) using a cross-over model, thus fulfilling the preferred aim of minimising the number of participants in the study.

For a randomise-by-individual approach, assuming a confidence level of 95% and a power of 80%, and anticipating the expected non-infestation rates to be 65% for Octanediol 1% Solution and 30% for the placebo, the required sample size is therefore estimated as 34 subjects per treatment. However, this study will operate a “hybrid” randomization in that only one person from each household will be randomized (index case) and all others in the house will be offered treatment when infestation arises but will continue to potentially act as a source of reinfestation. This approach reduces possible confounding issues of enrolling all members, in which some households will have all members on one intervention but others will have a mixture of active and placebo interventions. Therefore, for each participant on each arm of the cross-over the familial risk of reinfestation should be similar in this respect.

Sample size table for 2 hazard ratios in survival analysis

| | 0.05 | 0.10 | 0.15 | 0.20 | 0.25 | 0.30 | 0.35 | 0.40 | 0.45 | 0.50 | 0.55 | 0.60 | 0.65 | 0.70 | 0.75 |
|------|------|------|------|------|------|------|------|------|------|------|------|------|------|------|------|
| 0.10 | 496 | | | | | | | | | | | | | | |
| 0.15 | 173 | 963 | | | | | | | | | | | | | |
| 0.20 | 99 | 295 | 1414 | | | | | | | | | | | | |
| 0.25 | 69 | 155 | 406 | 1826 | | | | | | | | | | | |
| 0.30 | 53 | 100 | 203 | 504 | 2186 | | | | | | | | | | |
| 0.35 | 43 | 73 | 127 | 245 | 588 | 2486 | | | | | | | | | |
| 0.40 | 36 | 57 | 90 | 149 | 280 | 656 | 2723 | | | | | | | | |
| 0.45 | 32 | 47 | 68 | 103 | 167 | 307 | 708 | 2894 | | | | | | | |
| 0.50 | 28 | 39 | 54 | 77 | 114 | 181 | 326 | 743 | 2997 | | | | | | |
| 0.55 | 26 | 34 | 45 | 60 | 83 | 121 | 190 | 338 | 761 | 3032 | | | | | |
| 0.60 | 24 | 30 | 38 | 49 | 65 | 88 | 126 | 195 | 343 | 761 | 2999 | | | | |
| 0.65 | 22 | 27 | 33 | 41 | 52 | 67 | 90 | 128 | 195 | 339 | 744 | 2897 | | | |
| 0.70 | 21 | 25 | 30 | 36 | 43 | 54 | 69 | 91 | 127 | 192 | 328 | 711 | 2727 | | |
| 0.75 | 20 | 23 | 27 | 31 | 37 | 44 | 54 | 68 | 89 | 123 | 183 | 310 | 660 | 2490 | |
| 0.80 | 19 | 22 | 24 | 28 | 32 | 37 | 44 | 54 | 66 | 86 | 116 | 171 | 284 | 592 | 2186 |
| 0.85 | 18 | 20 | 23 | 25 | 28 | 32 | 37 | 43 | 52 | 63 | 80 | 107 | 154 | 250 | 508 |
| 0.90 | 18 | 19 | 21 | 23 | 26 | 28 | 32 | 36 | 42 | 49 | 59 | 73 | 95 | 133 | 209 |
| 0.95 | 17 | 19 | 20 | 21 | 23 | 25 | 28 | 31 | 34 | 39 | 45 | 53 | 64 | 81 | 108 |

This estimate of the likely numbers in relation to application of the Octanediol 1% Solution active material for 6 weeks followed by placebo for 6 weeks assumes that the potential rate of contact and reinfestation is more or less linear so that, where it was estimated from past data that a likely reinfestation rate would be approximately 4 per week for the whole population, the possible number of new cases would be 24 over the 6 weeks of one half term, or 12 cases per treatment if neither had any effect. However, if the test preparation is effective this number of cases could be reduced by approximately 60% resulting in 5 cases. This difference offers essentially similar powering to that of a parallel group calculation, although the statistical significance would be reduced overall if the reinfestation rate were to be no greater than 4 per week.

Analytical Methods:

The primary endpoint analysis is the comparison between the Octanediol 1% Solution and placebo in the frequency of not developing an infestation, with the difference between the two study treatment arms tested using the "intention-to-treat" population. Secondary endpoint analyses will be the frequency (number) of instances of reinfestation and safety of the product and participant acceptance.

Analyses will be conducted based on both the "intention-to-treat" and the "per-protocol" populations.

As this is a cross-over study with equal numbers in each treatment arm it is appropriate to analyse efficacy using a Kaplan-Meier survival analysis. This analysis will compare the time to first infestation for each individual in each arm of the crossover, in which the time to first infestation is taken as the "survival" endpoint. This will essentially address the three first analytical tasks set out in section 3.3, although point 1. will also be addressed in other analyses.

It is not considered that censoring will present as a major issue during the first half term period and, if it does occur at all, right censoring from the second half term is the likely outcome. For these data it would be appropriate to use the log-rank test to analyse in relation to time to first infestation. Comparison of the "survival" curves would probably be more appropriate in this case using the Brand and Altman approach and hazard ratio curves rather than conventional Kaplan-Meier curves (Bland and Altman, *BMJ*, 2004, 328, 1073).

However, if no censoring occurs, it may be more appropriate, because the primary outcome measure is no evidence of active head louse infestation, that the primary analysis method could additionally use the McNemar's test on these binary outcome (evidence/no evidence of active head louse infection during the treatment period) data as a simple method to address point 1. of section 3.3, to answer the question as to whether the Octanediol 1% Solution is able to prevent establishment of a head louse infestation.

In addressing point 4. of section 3.3, which may potentially result in a ranked variable, from how many times each individual becomes infested over the course of each arm of the crossover, the Wilcoxon signed rank test will be used for the paired data derived from the time spent in each arm of the study by each participant.

Because this is a cross-over study there will be no conventional comparison of difference between groups in baseline characteristics. However, the two arms will be tested for comparability of some baseline characteristics, such as presence of infestation, and presence of infestation in other household members at the start of the study and at the commencement of the "wash-out" cross-over treatment. For these comparisons, and comparisons of safety, and acceptability data will be tested using Fisher's exact test for yes/no variables and the Wilcoxon signed rank test for paired data, or Mann-Whitney U test for unpaired, ranked variables.

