2.3.3.6 Assessment Analysis

Definition of "infested"

It is anticipated that during the course of the study a high proportion of participants will have encounters with head lice. It is also anticipated that the Octanediol 1% solution will have a sufficient inhibitory effect on the viability of the lice that they will not be able to establish an ongoing infestation. However, this effect is not immediate and may take effect over the course of several days. Therefore, it is quite conceivable that at some point a participant may be examined and one or more apparently viable lice may be discovered. Such an event should not be considered to be a failure of the treatment and at that stage no additional intervention should be undertaken. Instead the participant should continue with the routine and at the next examination if apparently viable lice are discovered again, especially if the numbers have increased, a therapeutic intervention using the standard of care treatment should be given.

At this point, or at any other stage of the study, if ≥ 5 adult lice are found or if any stage 1 or stage 2 nymphal lice are found, it will be considered that an infestation has established and the standard of care treatment (Hedrin Once liquid gel) will be given.

Evaluation of lice recovered

Any lice fixed into the CRF during the course of the study will be examined under the microscope to establish the sex and/or stage of development of the insects. It is expected that if lice are found during the monitoring period they will be adult or third stage nymphs that have newly migrated to the head. The presence of small lice (nymphs) will be evidence that lice had established before being found and had not been sufficiently affected by the treatment regimen that they were not inhibited from laying eggs, which in turn were not prevented from developing. All CRF pages bearing lice will be archived along with the other CRF documents, the lice fixed with tape constituting a permanent record, in much the same manner as a microscope slide.

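### Section 3.4 counts possible contacts as new cases, and its own forecast of 12 v 5 cases per treatment does not support the power it claims

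*Protocol*

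**What the plan says.** All of the sizing is in Protocol section 3.4, under Sample Size Determination.

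- **Formal sample size.** It is set by "anticipating the expected non-infestation rates to be 65% for Octanediol 1% Solution and 30% for the placebo", and "the required sample size is therefore estimated as 34 subjects per treatment".
- **Source of the placebo rate.** A louse-free rate of 25% to 35% over a school term is given for the comparison group: "whereas people at similarly high risk of infestation who take no action, or as in this study use placebo".
- **Weekly rate.** Past study data on when people contracted lice are said to support 3 to 5 reinfestations per person per year, which the text calls an infestation rate. This is converted to 3.6 to 4 possible events per week for the cohort. The next sentence qualifies it: "This doesn't mean that they will get lice but rather that they could come into contact with someone who does have them".
- **Event forecast.** After the table, 4 per week is used directly, with the count supposing that both preparations are inert: "the possible number of new cases would be 24 over the 6 weeks of one half term, or 12 cases per treatment if neither had". A reduction of about 60% takes 12 to 5. The text concludes that the power is much the same as for a parallel-group calculation, and adds that significance would be reduced if the rate were no greater than 4 per week.
- **Endpoint.** Section 2.3.3.6 says of a first find of lice: "Such an event should not be considered to be a failure of the treatment and at that stage no additional intervention should be undertaken". An infestation needs lice again at the next examination, 5 or more adults, or any stage 1 or 2 nymph.

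**The concern.** Section 3.4 gives one number two meanings. As contacts, 4 per week must be multiplied by the chance that a contact becomes an established infestation before it can be called cases, and no such fraction is applied. As infestations, the sentence denying that participants will get lice is wrong. Either way, the power statement rests on 12 v 5, and neither that pair nor its control rate agrees with the calculation it is compared with.

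Interpretation is at stake. If control infestations are too few, a null result could be read as lack of effect when the trial could not have shown one, and the protocol would have told its readers that power was adequate.

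**Working it through.** **1. The formal sample size reproduces.** Inputs: 30% v 65% louse free, alpha 0.05, power 80% (section 3.4). Sidedness is not stated; two-sided reproduces the table. Freedman log-rank:

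- Hazard ratio = ln 0.65 / ln 0.30 = 0.358.
- Events = (1.960 + 0.842)² × (1.358/0.642)² = 35.1.
- N = 35.1 / (1 − 0.475) = 66.8, so 67. This is the table cell, and gives 34 per treatment.

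**2. The forecast reproduces.** 4 × 6 = 24; 24/2 = 12; 12 × 0.4 = 4.8, about 5.

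**3. Power of the forecast.** Two proportions, two-sided 5%, pooled null variance, each case counted as a different participant:

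Power = Φ{ [ |p1 − p2|√n − 1.96√(2p̄(1 − p̄)) ] / √(p1(1 − p1) + p2(1 − p2)) }

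- 12 v 5 of 34: p1 = 0.353, p2 = 0.147, p̄ = 0.25. Power = Φ[(1.2005 − 1.2002)/0.595] = 50%. At 12 v 4.8 it is 53% (51% by Freedman with 68 in total).
- Both half terms, 24 v 10 of 68, unpaired: Φ[(1.698 − 1.200)/0.595] = 80%. At 24 v 9.6 it is 82%.
- Both half terms, exact McNemar at 24 v 9.6, assuming within-person independence: discordant probabilities are 0.353 × 0.859 = 0.303 and 0.141 × 0.647 = 0.091. Power is about 76%.

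**4. The two control rates disagree.** 30% louse free means 0.70 × 34 = 23.8 control cases. The forecast has 12 of 34, which is 35% infested and 65% free.

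**5. The weekly rate does not match its source.** In 68 people, 3 to 5 per person-year is 68 × 3/52 = 3.9 to 68 × 5/52 = 6.5 per week, not 3.6 to 4. Per treatment and half term that is 34 × 3 × 6/52 = 11.8 to 34 × 5 × 6/52 = 19.6.

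With every event a case, the louse-free proportion is exp(−rate × weeks/52): 71% to 56% at 6 weeks and 50% to 32% at 12 weeks. So 30% is approached only at the top rate over a full term, whereas each treatment period lasts 6 weeks.

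**6. Effect of conversion below 100%.** The protocol gives no fraction, so this range is an assumption. Rate 4 per week, 60% reduction:

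| Events meeting 2.3.3.6 | Cases per treatment, one half term | Power, 34 per treatment | Power, both periods, exact McNemar |
|---|---|---|---|
| 100% | 12 v 4.8 | 53% | about 76% |
| 75% | 9 v 3.6 | 39% | about 59% |
| 50% | 6 v 2.4 | 26% | about 36–37% |

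**7. If the placebo louse-free rate is higher than 30%.** Freedman power at N = 68:

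| Placebo louse free | Planned hazard ratio 0.358 kept | Active held at 65% |
|---|---|---|
| 35% | 77% | 68% |
| 40% | 73% | 54% |
| 45% | 69% | 38% |

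The last column also shrinks the effect (hazard ratio 0.41, 0.47 and 0.54), so it mixes two changes.

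**The case against.** **The sample size does not come from the contact count.** This stands. N = 34 rests on 30% v 65% and reproduces; 12 v 5 is a later cross-check. A reader might infer that the sample size is miscalculated or that the trial is underpowered on its planning rates. The documents do not support that: if 30% v 65% held in each 6-week period, exact McNemar power with 68 people would be about 98%.

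**The 12 cases are not a maximum.** This also stands. A reader might take 12 (or 24) as an upper bound because contacts outnumber infestations. But 12 lies at the bottom of the 11.8 to 19.6 that the protocol's own annual rate allows, and over both half terms each treatment would have 24 at 4 per week.

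**The rate may already be a rate of infestation.** It is said to come from data on people who contracted lice. That is a fair reading, and it makes the passage self-contradictory. The contact reading cannot simply be imposed.

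**The text is hedged.** It speaks of a possible number of cases, concedes reduced significance at no more than 4 per week, and places the sample size near the lower end of its 62 to 90 range. But the caveat gives no figure, and 4 per week is the planning rate itself, so it does not rescue the power statement.

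**Placebo at the no-action rate is a declared assumption.** This stands. It is tempting to say that twice-weekly combing at application, weekly detection combing and household care ("all others in the house will be offered treatment when infestation arises") must all lower the placebo rate. The documents give no effect for any of these. Weekly inspection could instead raise detection, and the same sentence says household members remain a possible source of reinfestation.

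**Conclusion.** The concern holds as a failure of a stated power property and as a contradiction over what the weekly rate measures. Power for 12 v 5 of 34 is about 50%, against the 80% of the calculation it is said to match. That gap exists at 100% conversion, so it comes from the mismatch between 12 and about 24 control cases and not from contacts. Pooling both half terms brings power to about 80% unpaired or 76% paired, but only if every event meets 2.3.3.6. Any lower conversion reduces it further.

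The size of that further loss cannot be derived from the documents. The 50% to 100% range is an assumption, as are within-person independence and one case per person per period.

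**What to change.** All changes are in section 3.4:

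1. State whether 4 per week means contacts or established infestations as defined in 2.3.3.6, and use that meaning in both places.
2. Correct the weekly rate to agree with 3 to 5 per person-year in 68 people (3.9 to 6.5 per week), or revise the annual rate.
3. Reconcile the forecast of 12 control cases with the 30% louse-free rate, saying whether that rate applies to a 6-week period or a school term.
4. Replace the statement of similar power with expected cases and power over an assumed conversion range, as in the table in step 6. Do not describe 12 or 24 as an upper bound.
5. Say explicitly that giving placebo users the no-action rate is an assumption. If power is shown for higher placebo louse-free rates, give it at the planned hazard ratio too.

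The cost is wording and a short table. The stated power becomes less favourable. Recruitment, visits and care do not change.

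### The 80% power and 34 per treatment were not derived for the six-week cross-over, and the protocol's own case forecast does not support them

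*Protocol*

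**What the plan says.** All of this is in Protocol section 3.4, Sample Size Determination, unless noted.

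- **Rates and their time base.** The section expects that "regular use may prevent an infestation from developing in about 60%-70% of users over a period of a school term", and that people on placebo "might be expected to go through a school term without infestation in about 25%-35% of cases".
- **Sample size.** Taking 65% louse-free on active and 30% on placebo, with 95% confidence and 80% power, the section concludes that "the required sample size is therefore estimated as 34 subjects per treatment". The figure is read from a table for two survival proportions in which each cell is the total for both groups.
- **Event rate.** From 3 to 5 reinfestations per person per year the section derives a weekly figure, "i.e. a risk of about 3.6-4 possible reinfestation events per week for the whole study population". It adds that these are possible contacts and need not become infestations.
- **Forecast.** At about 4 per week it expects 24 cases in one half term, or 12 per treatment with no effect, falling by about 60% to 5 on active. Its conclusion is "This difference offers essentially similar powering to that of a parallel group calculation". It then concedes some loss of significance should the weekly rate not exceed 4.
- **Exposure.** Sections 1.1 and 2.3.3.4 give six weeks on each product for every participant. Sections 1.4 and 2.1.1 equate the 12 weeks with roughly one school term.

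**The concern.** Section 3.4 describes two different trials. The sample size assumes 30% louse-free on placebo. The forecast that follows, 12 cases among 34, leaves about 65% louse-free on placebo. Both cannot be the planned outcome, and no power is calculated for the cross-over that will be run. The caveat about significance applies at a rate no greater than 4 per week, which is the rate the forecast assumes.

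What is at stake is how the result is read. If 80% is taken as the power of the trial, a null result counts as fairly strong evidence against the product. At the protocol's own forecast it may deserve much less weight.

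**Working it through.** **Inputs from the protocol:** 65% and 30% louse-free per term; term about 12 weeks; six weeks per product; 68 participants; about 4 events per week; 12 versus 5 cases per half term; reduction of about 60%; 3-5 events per person-year. **Assumed:** two-sided 0.05 (sidedness is not stated, but this reproduces the table), and the within-person correlation, which is not given.

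**1. Reproduce the stated figure.** The table follows Freedman's log-rank formula, with HR = ln(S active)/ln(S placebo):

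- HR = ln 0.65 / ln 0.30 = 0.358
- Events = (1.960 + 0.842)² × ((1 + HR)/(1 − HR))² = 35.1
- N = 2 × 35.1 / (2 − 0.65 − 0.30) = 66.8; the table shows 67, hence 34 per group

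Power = Φ(√events × (1 − HR)/(1 + HR) − 1.960). With 68 people, events = 68 × 0.525 = 35.7 and power is 80.7%. So the 80% belongs to two separate groups of 34.

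**2. Same rates, actual design.** If 65% versus 30% held within six weeks, 68 people on each product (136 person-periods) would give 71.4 events and 98% power.

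**3. Rescale the term rates to six weeks at constant hazard.** √0.30 = 0.548 and √0.65 = 0.806; HR stays 0.358.

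- 34 per group: 34 × (0.452 + 0.194) = 22.0 events, power 60%
- 68 per product: 43.9 events, power 88%

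**4. The protocol's forecast.** 12/34 and 5/34 infested is 64.7% and 85.3% louse-free, so HR = 0.365 and (1 − HR)/(1 + HR) = 0.465.

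- One half term, 17 events: Φ(√17 × 0.465 − 1.960) = Φ(−0.04) = 48%
- Both half terms, 24 versus 10 of 68, 34 events, periods treated as independent: Φ(0.75) = 77%

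The protocol's table at 0.85 versus 0.65 asks for 154 in total. One half term supplies 68 and the full cross-over 136 person-periods.

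**5. Sensitivity over both half terms at about 4 per week.** The second column assumes every case is a different child. The third treats 4 per week as a rate that includes repeats: 24/68 = 0.353 per child per six weeks, so exp(−0.353) = 70.3% louse-free on placebo and exp(−0.4 × 0.353) = 86.8% on active, with 68 × (0.297 + 0.132) = 29.2 first infestations at HR 0.40.

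| Method, 68 per product | 24 vs 10 children | First infestations |
|---|---|---|
| Freedman, independent periods | 77% | 64% |
| Two proportions, independent periods | 80% | – |
| Schoenfeld, independent periods | 84% | 70% |
| McNemar, correlation 0 (exact to asymptotic) | 73-81% | 57-67% |
| McNemar, correlation 0.2 (assumed) | 83-89% | 68-76% |
| McNemar, correlation 0.4 (assumed) | 94-96% | 81-87% |

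**6. The weekly rate.** 68 × 3/52 = 3.9 and 68 × 5/52 = 6.5. Working back, 3.6 × 52/68 = 2.8 and 4 × 52/68 = 3.1 per person-year, so the stated 3.6-4 sits at or below the bottom of the 3-5 range. At 5 per person-year: 5 × 6/52 = 0.577, so 56% versus 79% louse-free, 43.8 events, and 81% by the table's method.

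**The case against.** The strongest reply is that the cross-over must be judged over both halves. There, 24 versus 10 of 68 gives 73-84% across standard tests even with no correlation, so a claim of power similar to the parallel calculation is not absurd. Pairing is the protocol's stated reason for the design, and positive correlation would raise power further. The section also admits that the risk is largely unknown, and section 1.1 calls the trial proof of concept. All of this stands, and it rules out several stronger readings:

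- **That the trial has 48% power.** That figure, like Fisher's p = 0.09 for 12/34 versus 5/34, describes one half term as a parallel trial.
- **That power lies between 64% and 77%.** Those are two results from one unpaired formula. Step 5 gives values on both sides of them.
- **That no assumption in the protocol reaches 80%.** Steps 2, 3 and 6 give 98%, 88% and 81%.
- **That the mixed time base causes the shortfall.** On its own it leaves the full cross-over at about 88%.
- **That the 62-90 participant range in section 3.4 is wrong.** It depends on table shading that cannot be seen in the text available.

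The reply does not rescue the sentence itself. The sentence rests on 12 versus 5 in one half term, and no cross-over calculation is shown. Nor does pairing help only in one direction. If risk varies between children while the total stays at 4 per week, repeats concentrate in fewer children. With an assumed gamma frailty variance of 0.25-2, McNemar power is about 44-65%.

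**Conclusion.** The point holds in this form. The 80% is correctly computed for a parallel comparison at 65% versus 30%, but it is not the power of the planned six-week cross-over. The forecast printed beside it implies about 65% versus 85% louse-free and does not support the claim of similar powering.

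The protocol leaves the power of the design undetermined. At about 4 per week with no within-person correlation it is roughly 55-85%, depending on the test and on whether repeat cases in one child are counted. It is about 68-89% at an assumed correlation of 0.2, and about 81% by the table's method at 5 per person-year. It is lower if the possible events do not all become infestations, or if they cluster in a few children. The conversion to 3.6-4 per week is a plain arithmetic error and depends on no modelling choice.

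**What to change.** Amend Protocol section 3.4:

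1. State the louse-free proportions for six weeks, with 68 participants on each product.
2. Replace 3.6-4 events per week by 3.9-6.5.
3. Delete the claim of similar powering, and say that the 80% was not derived for the six-week cross-over.
4. Give power as a range by event rate, test, counting of repeat cases and within-person correlation, with the assumed values labelled as such. A single replacement figure would be no better supported than the 80%.

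The cost is wording only. The number of participants, the endpoints and the conduct of the trial do not change. The downside is a stated power that is less favourable and less certain.
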